Studies have shown that ACZ administered as a single 1000 mg IV bolus transiently enhances cerebral perfusion in healthy subjects (Sullivan et al., 1987; Vagal et al., 2009). Subjects challenged with IV ACZ had between a 30% to 60% increase in cerebral blood flow, as measured by Xenon-enhanced computed tomography scan, within 15 minutes of IV bolus (Sullivan et al., 1987). Another study using ultrasonography demonstrated that enhanced perfusion was sustained for at least 30 minutes with return to baseline measures within one hour (Hartkamp et al., 2012). This same dose and route of administration will be used in subjects with MS to determine the transient change to cerebral perfusion as quantified using MRI metrics as described in section 2.2.

Though ACZ IV transiently enhances cerebral perfusion, longer-term changes would be required to potentially impact lesion evolution. Daily or divided-daily infusions necessitate chronic IV access, pose increased risk to the patient and are impractical. Oral ACZ has been shown to also increase cerebral perfusion in patients with other neurologic disorders ("Acetazolamide Tablets | Drug Summary | PDR.net," n.d.) and might prove a practical and effective alternate chronic therapy for patients with MS.

ACZ has been used in daily divided doses up to a maximum of 4000 mg per day to treat pseudotumor cerebri (NORDIC Idiopathic Intracranial Hypertension Study Group Writing Committee et al., 2014). Participants in Stage 1b of this study will be given escalating divided doses of oral ACZ up to 1500 mg per day to determine both the magnitude of change to cerebral perfusion with each dose and define the optimum dose(s) for additional studies. In the final stages of this study (stage 2a and 2b), subjects will be treated with ACZ, as determined in stage 1b, for six consecutive months to determine if long-term change to cerebral perfusion alters the evolution of MS plaques into persistent black holes.

Rationale for Study Population

Multiple sclerosis affects predominantly persons between 15 and 55 years of age with females being nearly four-times as likely to be diagnosed with disease as males (Koch-Henriksen and Sørensen, 2010; Orton et al., 2006; Reingold, 2002). MS in the paediatric population is now better recognized and has been shown to differ from that in the adults in both clinical and radiologic presentation and evolution (Ghassemi et al., 2014; Renoux et al., 2007).

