Stage 1b - Changes in cerebral perfusion will likely need to be sustained for prolonged periods to impact lesion evolution. Participants in this stage of the study will be given escalating divided doses of oral ACZ up to 4000 mg per day to determine both the magnitude of change to cerebral perfusion with maintenance daily oral ACZ therapy and to define the optimum dose(s) for additional studies.

Subjects will undergo MRI using pCASL prior the start of each bi-monthly regimen of ACZ as well as on the day of drug discontinuation. The magnitude of change in CBF will be determined for various oral ACZ doses as well as for various cerebral regions

Stage 2a – Safety/Tolerability & Kinetics of Treatment Effect

This stage will continue to gather information about whether daily oral ACZ is tolerated and the kinetics of the treatment effect. Patients continue on the same dose for 12 consecutive weeks and undergo repeat imaging at predetermined intervals. Sustained treatment over a short duration will allow us to rapidly determine whether sustained treatment with ACZ can alter cerebral blood flow and will provide a go/no-go for future studies using this drug/paradigm. In this stage, all subjects will receive baseline pCASL and DSC MRI, will start oral ACZ continued for 12 consecutive weeks and undergo repeat imaging at predetermined intervals. MRI scans and clinical evaluations will be obtained every 6 weeks with contrast-based scans repeated at 12 weeks. As previously stated, DSC provides measurements of not only CBF but also blood volume (CBV) and transit time of blood (MTT). It is possible that in addition to changes in blood flow, the amount or rate of flow is altered with ACZ and may be an important mechanism to tissue repair. DSC techniques will provide information that cannot be obtained by using pCASL alone that might be important to determine how blood flow is altered with ACZ.

In addition, we will use advanced MRI techniques to also quantify tissue oxygen extraction before and after ACZ therapy as well as determine the metabolic rate of oxygen consumption in various tissues.

Stage 2a – Safety/Tolerability & Kinetics of Treatment Effect

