During the dose escalation, in addition to issues of tolerability, subjects will be monitored at each transition point for the following specific serious AEs: paraesthesia, change in taste, accelerated change in blood pressure or fluid retention. Any subject with serious AEs will be withdrawn from the study. Patients with persistent serious AEs will be treated using standard medical practice.

STUDY POPULATION

List the number of subjects to be enrolled.

This exploratory study is designed to evaluate the long-term effects of oral ACZ on CBF in adult subjects with MS. We will enroll 100 MS subjects between the age of 18 and 55 without history of cerebrovascular disease or glaucoma.

There are several studies suggesting that MS lesions in the pediatric population differ from that typically seen in the adult population (Ghassemi et al., 2014; Renoux et al., 2007). To minimize potential confounding variables, all stages of the study will recruit only adult subjects with MS.

All subjects will be recruited from patients seen at the MS clinic located at the University of Texas Professional building (UTP) Neurology practice

Information about the study will be available on the UT Neurology web site and in print format at the UTP MS clinic.

Informed consent will be obtained from each participant prior to entry and, for subjects who elect to

participate in multiple parts of the study, prior to each stage.

Criteria for Recruitment

Subjects who wish to participate in either stage of the study will be evaluated by the principle investigator to determine if they meet inclusion and exclusion criteria. A thorough medical history will be performed to determine if any pre-existing cardiovascular disease or glaucoma is present. Subjects whose history is unknown will be encouraged to obtain evaluation by a primary care physician and eye-care specialist prior to recruitment. In addition, available blood tests, performed within six months of study entry, will be reviewed to determine if any renal or hepatic dysfunction is present.

Potential subjects with historical or laboratory evidence to suggest dysfunction in one of the above clinical systems will be excluded from study participation. As the rate of these comorbidities is low in a young population, we do not anticipate large numbers of failures at this stage of screening.

Inclusion Criteria

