Subjects will receive 1 gram bolus of IV ACZ and a second scan using pCASL sequences will be obtained within 15 minutes of infusion. Subjects will remain in the MRI gantry and receive a third scan to determine CBF at 30 minutes from time of infusion. Subjects will then be removed from the MRI gantry and allowed a break.

Subjects will again be placed on the MRI gantry and scout, 3DT1 and pCASL sequences obtained within 120 minutes from time of ACZ infusion. Subjects will then be removed from the MRI gantry and allowed a break. A final scan will be performed using the same sequences within 240 minutes from time of ACZ infusion.

Stage 1b:

Screening Visit – Subjects will receive a complete medical and neurological examination. In addition, all subjects will obtain CBC, CMP and, if female, urine pregnancy test.

Visit 1 – Subjects will receive non-contrast MRI brain using sequences previously described to ensure proper orientation and registration (scout, 3DT1), sequences necessary for segmentation using MRIAP (2D dual echo, 2D fluid-attenuated inversion recovery [FLAIR]) and pCASL sequences to determine CBF at baseline. Subjects will begin taking 250 mg oral ACZ twice daily and continue for two weeks. Subjects will be encouraged to call the PI with any adverse events (see sections 2.4b and 7.1.2) while on study drug.

Visit 2 – Prior to dose-escalation, subjects will receive non-contrast MRI brain sequences as described above to measure effect of previous oral daily divided dose of ACZ on CBF. Upon completion of MRI, subjects will begin taking 500 mg oral ACZ twice daily and continue for two weeks. Subjects will be encouraged to call the PI with any adverse events (see sections 2.4b and 7.1.2) while on study drug.

Visit 3 – Prior to dose-escalation, subjects will receive non-contrast MRI brain sequences as described above to measure effect of previous oral daily divided dose of ACZ on CBF. Upon completion of MRI, subjects will begin taking 1000 mg oral ACZ twice daily and continue for two weeks. Subjects will be encouraged to call the PI with any adverse events (see sections 2.4b and 7.1.2) while on study drug.

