Visit 4 – Prior to dose-escalation, subjects will receive non-contrast MRI brain sequences as described above to measure effect of previous oral daily divided dose of ACZ on CBF. Upon completion of MRI, subjects will begin taking 1500 mg oral ACZ twice daily and continue for two weeks. Subjects will be encouraged to call the PI with any adverse events (see sections 2.4b and 7.1.2) while on study drug.

Visit 5 – Prior to dose-escalation, subjects will receive non-contrast MRI brain sequences as described above to measure effect of previous oral daily divided dose of ACZ on CBF. Upon completion of MRI, subjects will begin taking 2000 mg oral ACZ twice daily and continue for two weeks. Subjects will be encouraged to call the PI with any adverse events (see sections 2.4b and 7.1.2) while on study drug.

Visit 6 – Subjects will receive non-contrast MRI brain sequences as described above to measure effect of previous oral daily divided dose of ACZ on CBF. Upon completion of MRI, subjects will discontinue use of ACZ.

Stage 2a:

c)

Screening Visit – Subjects will receive a complete medical and neurological examination and obtain screening EDSS evaluation. In addition, all subjects will obtain CBC, CMP and, if female, urine pregnancy test.

Visit 1 – Subjects will receive MRI brain with and without gadolinium contrast utilizing the following sequences in the order listed:

Scout and 3D T1-weighted images to ensure proper orientation and registration 2D dual echo, 3D FLAIR necessary for segmentation

Muti-shell DWI (DTI sequences)

A single shot 2D echo-planar imaging (EPI) for pCASL-based measures of CBF

2D T1-weighted images prior to Gd administration

DSC sequence for measures of CBF, CBV, MTT

2D T1-weighted images after Gd administration

In addition to segmenting MS lesion (T2 hyperintense), we are able to segment T1 pre- and post-Gd lesion volumes. Images obtained at the site at UT are routinely subject to review by a radiologist who is not further involved in image analysis.

Visit 2 – Subjects will receive a complete medical and neurological examination, MSFC & EDSS evaluation as well as patient-reported clinical disability measures (MFIS & MSWS-12) and will be asked questions to ascertain tolerability to daily therapy. All subjects will obtain MRI brain without gadolinium contrast utilizing the sequences described above except for DSC sequence.

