Visit 7 – Subjects will receive a complete medical and neurological examination, MSFC & EDSS evaluation as well as patient-reported clinical disability measures (MFIS & MSWS-12) and will be asked questions to ascertain tolerability to daily therapy. All subjects will obtain MRI brain without gadolinium contrast utilizing the sequences described above except for DSC sequence.

Visit 8 – Subjects will receive a complete medical and neurological examination, MSFC & EDSS evaluation as well as patient-reported clinical disability measures (MFIS & MSWS-12) and will be asked questions to ascertain tolerability to daily therapy. All subjects will obtain MRI brain with and without gadolinium contrast utilizing the sequences described above.

Visit 9 – Subjects will receive a complete medical and neurological examination, MSFC & EDSS evaluation as well as patient-reported clinical disability measures (MFIS & MSWS-12) and will be asked questions to ascertain tolerability to daily therapy. All subjects will obtain MRI brain without gadolinium contrast utilizing the sequences described above except for DSC sequence.

Visit 10 – Subjects will receive a complete medical and neurological examination, MSFC & EDSS evaluation as well as patient-reported clinical disability measures (MFIS & MSWS-12) and will be asked questions to ascertain tolerability to daily therapy. All subjects will obtain MRI brain with and without gadolinium contrast utilizing the sequences described above. Upon completion of the brain MRI, all subjects will be instructed to discontinue assigned treatment.

Visit 11 – Subjects will receive a complete medical and neurological examination, MSFC & EDSS evaluation as well as patient-reported clinical disability measures (MFIS & MSWS-12) and will be asked questions to ascertain any other AEs after discontinuation of therapy. All subjects will obtain MRI brain without gadolinium contrast utilizing the sequences described above except for DSC sequence.

Subjects will be contacted by telephone or email monthly to document tolerability and encouraged to report any AE occurring with drug at any point during the study.

For any part of the study, a subject whose CBC or CMP is not at or near baseline values will repeat these blood tests.

a. Final Study Visit:

The final study visit will be used to document any potential adverse event associated with treatment arm, not previously documented.

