Acetazolamide treatment may cause electrolyte imbalances, including hyponatremia and hypokalemia, as well as metabolic acidosis. Therefore, periodic monitoring of serum electrolytes is recommended. Particular caution is recommended in patients with conditions that are associated with, or predispose a patient to, electrolyte and acid/base imbalances, such as patients with impaired renal function (including elderly patients; see PRECAUTIONS, PRECAUTIONS, Geriatric Use), patients with diabetes mellitus, and patients with impaired alveolar ventilation.

Some adverse reactions to acetazolamide, such as drowsiness, fatigue, and myopia, may impair the ability to drive and operate machinery.

Laboratory Tests

To monitor for hematologic reactions common to all sulfonamides, it is recommended that a baseline CBC and platelet count be obtained on patients prior to initiating acetazolamide therapy and at regular intervals during therapy. If significant changes occur, early discontinuance and institution of appropriate therapy are important. Periodic monitoring of serum electrolytes is recommended.

Drug Interactions

Aspirin:

See WARNINGS

Acetazolamide modifies phenytoin metabolism with increased serum levels of phenytoin. This may increase or enhance the occurrence of osteomalacia in some patients receiving chronic phenytoin therapy. Caution is advised in patients receiving chronic concomitant therapy. By decreasing the gastrointestinal absorption of primidone, acetazolamide may decrease serum concentrations of primidone and its metabolites, with a consequent possible decrease in anticonvulsant effect. Caution is advised when beginning, discontinuing, or changing the dose of acetazolamide in patients receiving primidone.Because of possible additive effects with other carbonic anhydrase inhibitors, concomitant use is not advisable.

Acetazolamide may increase the effects of other folic acid antagonists.

Acetazolamide decreases urinary excretion of amphetamine and may enhance the magnitude and duration of their effect.

Acetazolamide reduces urinary excretion of quinidine and may enhance its effect.

Acetazolamide may prevent the urinary antiseptic effect of methenamine.

Acetazolamide increases lithium excretion and the lithium may be decreased.

Acetazolamide and sodium bicarbonate used concurrently increases the risk of renal calculus formation.

Acetazolamide may elevate cyclosporine levels.

Drug/Laboratory Test Interactions

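### Stage 1b schedules no on-treatment CBC/CMP before the oral ACZ dose increases at Wk 2, 4 and 6

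*Combined protocol and SAP*

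**What the plan says.** **Laboratory schedule.** In the Stage 1b table, the CBC/CMP row is marked at Day -7 and Wk 8 and is blank at Wk 0, 2, 4 and 6. The Stage 1b text under Study Visits and Procedures mentions these tests once, at screening: "all subjects will obtain CBC, CMP and, if female, urine pregnancy test". A separate Blood Sample row is marked throughout Stage 1b with no assay given. The later-stage tables list it alongside CBC/CMP as a different row.

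**Dose ladder.** The table has four steps, from 500 to 2000 mg BID. The visit text has five and begins lower: "Subjects will begin taking 250 mg oral ACZ twice daily and continue for two weeks". Its last step is "Upon completion of MRI, subjects will begin taking 2000 mg oral ACZ twice daily and continue for two weeks". On the ceiling, Rationale for Doses Selected says "escalating divided doses of oral ACZ up to 1500 mg per day"; Rationale for Study Design and the Study Design summary both say "escalating divided doses of oral ACZ up to 4000 mg per day".

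**Checks at a dose step.** Before each increase the visit text orders an MRI. The safety text adds this: "in addition to issues of tolerability, subjects will be monitored at each transition point for the following specific serious AEs: paraesthesia, change in taste", followed by accelerated blood pressure change and fluid retention.

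**Other laboratory provisions.** A general rule says that "a subject whose CBC or CMP is not at or near baseline values will repeat these blood tests". The oral package insert reproduced under Trial Materials recommends that a "baseline CBC and platelet count be obtained on patients prior to initiating acetazolamide therapy and at regular intervals during therapy", and also advises periodic electrolyte checks. It gives no interval for either.

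**The concern.** The protocol's own adverse event list includes acid-base and electrolyte disturbance, and the package insert adds low sodium, low potassium and blood dyscrasias. The exclusion criteria keep out people with low sodium, low potassium, hyperchloremic acidosis or any history of cytopenia. The drug can therefore produce states that bar entry, yet the dose is raised without a scheduled recheck. That such a change may be present without symptoms is my clinical judgment; the documents do not say so. If it is, a check limited to tolerability and four clinical signs would miss it.

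Two things are at stake. One is subject safety: someone could move to a higher dose with an abnormality already present. The other is dose finding. Stage 1b is meant to identify the dose for later work, and a single test at the end of the ladder cannot show at which dose an abnormality began.

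**Working it through.** The plan states no figure to reproduce; the check is a count of scheduled draws against dose increases.

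**1. Table ladder.** Steps of 500, 1000, 1500 and 2000 mg BID start at Wk 0, 2, 4 and 6, which is 1000, 2000, 3000 and 4000 mg/day. There are three increases, on days 14, 28 and 42. On-treatment CBC/CMP falls on day 56 only. Increases with an earlier on-treatment result scheduled: **0 of 3**.

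**2. Age of the last scheduled result at each increase.** Screening is day -7, so 14 + 7 = 21, 28 + 7 = 35 and 42 + 7 = 49 days. Each time it is a pre-drug value.

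**3. Visit-text ladder.** Steps of 250, 500, 1000, 1500 and 2000 mg BID at two weeks each start at Wk 0, 2, 4, 6 and 8 and end at Wk 10. There are four increases, at Visits 2 to 5. Placement of the final draw is ambiguous, because the table labels Wk 8 as Visit 6 and has no Visit 5.
- Draw kept at Visit 6, when dosing stops: **0 of 4**.
- Draw placed by calendar at Wk 8, which becomes Visit 5 before the 2000 mg BID step: **1 of 4**.

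**4. Under the 1500 mg/day cap.** Only 1000 mg/day in the table fits, so there are no increases and no gap. In the visit text 500 and 1000 mg/day fit, so there is one increase, at Visit 2, with no on-treatment test scheduled before it. The two passages quoted for 4000 mg/day, the table itself and the Visit 5 text all exceed this cap.

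**5. Comparison with later stages.** Stages 2a, 2b and 3 mark CBC/CMP at every visit during treatment; Stage 1b marks it at 1 of 4 visits after the first dose. Much of that contrast is visit spacing, six-weekly against two-weekly. By calendar, the first on-treatment test comes at Wk 8 instead of Wk 6. Cumulative dose is a fairer yardstick:
- Stage 2a, at its first on-treatment test: 42 × 2000 mg = 84 g.
- Stage 1b table, at the three increases: 14 × 1000 mg = 14 g; 14 × (1000 + 2000) mg = 42 g; 14 × (1000 + 2000 + 3000) mg = 84 g.
- Stage 1b table, at its first on-treatment test: 14 × (1000 + 2000 + 3000 + 4000) mg = 140 g.

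Untested exposure is thus below the Stage 2a level at Wk 2 and Wk 4 and equal to it at Wk 6. What sets Stage 1b apart is that the daily dose exceeds the Stage 2a dose of 2000 mg/day from Wk 4, and that it rises between tests.

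**The case against.** The strongest reply is that the stage is small, supervised and perhaps finished. It has at most 10 subjects. History and physical examination is marked at every visit, the protocol cites earlier use of 4000 mg/day, and the team reports no serious AE in its own experience with IV or oral ACZ. The Safety Monitoring Plan lets treatment be adjusted or stopped, and Study Drug Administration requires stopping for reactions such as bone marrow depression. Entry is staggered over about twelve months, so early subjects' Wk 8 results could inform later escalations. Version 6 already names 1000 mg BID for Stages 2a and 2b, which suggests that Stage 1b may be complete.

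Most of this stands and limits the weight of the point. It does not supply the missing value. Stopping rules, dose adjustment and the repeat-test rule act on an abnormality that has been detected. Results from earlier subjects do not describe the subject about to be escalated, and a DSMB that meets twice a year is not a check within an 8-week course. The documents do not state that Stage 1b is closed.

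Four stronger readings are tempting and are not supported:
- **The schedule breaches the label.** The insert gives no testing frequency.
- **No on-treatment result could exist before an increase.** Unscheduled tests are not barred, and the Blood Sample assay is undefined, so it can neither be counted as a safety panel nor ruled out as one.
- **The gap holds under every version of the ladder.** Steps 3 and 4 of the working show exceptions.
- **The 1-of-4 count shows a lower testing standard than in later stages.** It largely reflects visit spacing.

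**Conclusion.** The point holds for scheduled tests: by the Stage 1b table, no on-treatment CBC/CMP precedes any of the three dose increases. On the visit text it precedes none of four, or one of four by calendar placement. This assumes that the 4000 mg/day ladder governs, as most of the protocol indicates, and that the Blood Sample row is not a safety panel. It is thin monitoring in a stage of at most 10 subjects, and the documents give no basis for estimating how often an abnormality would be missed. The change is worth making because it is cheap and the protocol itself names the risk. It matters only for subjects still to be escalated, and most before the steps above 1000 mg BID, the dose named for Stages 2a and 2b.

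**What to change.** For any subject still to be escalated:

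- Mark CMP (electrolytes) with CBC at Wk 2, 4 and 6 in the Stage 1b table, or at Visits 2 to 5 if the five-step text is kept, drawn with the blood sample already scheduled. If fewer draws are wanted, keep those before the steps above 1000 mg BID (Wk 4 and Wk 6 in the table). The two-week interval is my judgment: it follows the dose steps and is not a label frequency.
- Edit the Visit 2 to 5 sentences that start the next dose once the MRI is done. The treating physician should review the result first, and the subject should stay on the current dose until then.
- Add this use to the sentence on review of test results under Confidentiality of Data and Patient Records, which now confines the PI's review to exclusion, removal and AE documentation.

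Cost: one table row and a few sentences; at most 10 × 3 = 30 assays, or 10 × 4 = 40 on the five-step text. Allow for an extra tube, since the current assay is undefined. The downside is a possible short delay at each step, which lengthens the two-week period and separates the scan from the next dose.
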